### 9.4.4 Other efficacy outcome analyses

#### 9.4.4.1 Analysis of secondary efficacy outcomes in the cohort

##### 9.4.4.1.1 Count outcomes

Similar methods of analysis will be used to obtain crude and adjusted incidence ratios for secondary clinical outcomes.

##### 9.4.4.1.2 Time to first infection

The time to the first infection assessed among the cohort by PCR will be analysed using a Cox-proportional Hazards model. A shared frailty for study cluster and a 'fixed' effect coefficient for the study arm will be included. Results will be presented as the hazard ratio, 95% confidence intervals and *p*-values. The proportional hazards assumption will be checked using plotting and regressing the Schoenfeld residuals against time after model fitting. If the proportional hazards assumption is not

met, consideration of dose-response models with time-varying adherence measures will be considered, or alternative accelerated failure time models may also be considered.

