## 5 OBJECTIVES AND OUTCOMES

Table 1: Objectives and outcomes

5.1 PRIMARY OBJECTIVE AND OUTCOME	
Primary objective	Primary endpoint
To determine if ATSB deployment plus universal LLIN coverage is superior to universal LLIN coverage alone in reducing the case burden of clinical malaria in western Kenya	
 
The incidence rate of clinical malaria by the end of year-2, defined as current fever (axillary temperature of <math>\geq 37.5^{\circ}\text{C}</math>) or history of fever in last 48 hours and a positive rapid diagnostic test (RDT, pLDH or HRP2), in children aged 1-<15 years enrolled in the cohort study
 

5.2 SECONDARY OBJECTIVES AND OUTCOMES	
5.2.1 Efficacy	
Secondary objectives	Secondary endpoints
To determine if ATSB deployment plus universal LLIN coverage compared to universal LLIN coverage alone is superior in reducing malaria infection	
 
The time to first malaria infection assessed by PCR by the end of year-2, in children aged 1-<15 years enrolled in a cohort study
 
The incidence rate of malaria infection detected by RDT (pLDH) by the end of year-2, in children aged 1-<15 years enrolled in a cohort study
 
The prevalence of malaria infection diagnosed by RDT in continuous household surveys in participants aged <math>\geq 1</math> month.
 

To determine in ATSB deployment plus universal LLIN coverage compared to universal LLIN coverage alone reduces the clinical case burden in health facilities and communities	
 
The incidence rate of RDT or microscopy confirmed clinical malaria assessed through passive surveillance at health facilities and community-based surveillance by Community Health Volunteers serving the village-clusters
 

To determine if the rate of overall illness events differs in the ATSB deployment plus universal LLIN coverage arm when compared to the control arm	
 
The incidence rate of non-malaria illness in the cohort study
 
The incidence rate of all-cause sick visits assessed through passive surveillance at health facilities and community-based surveillance by community health volunteers
 

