## 7.7 ADHERENCE AND PROTOCOL DEVIATIONS

Both individual and cluster level adherence measures will be defined and pre-categorized prior to final analysis and used to categorize the per-protocol trial population. Since the intervention is deployed on a group basis rather than individually, adherence definitions will take account of this.

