### 7.7.2 Household-level adherence

Household-level adherence will be evaluated in the intervention cluster arms through ATSB monitoring visits. For each household, "expected ATSB-time" will be calculated by multiplying the total number of expected ATSBs hanging (2-3 ATSBs per structure) by the duration of time between visits (approximately four weeks). "Actual ATSB-time" will be calculated by multiplying the observed number of ATSBs during the monitoring visit by the duration of time they were hanging. The ratio of "actual ATSB-time" over "expected ATSB-time" will be expressed as a percentage and used as the measure to evaluate household-level adherence. For example, if a household has ten structures, and the intention is to have two ATSBs per structure, there should be 80 ATSB-weeks over four weeks (10x2x4). If the household had only one ATSB hanging on each structure between visits, the household would have an observed ATSB-time of 40 ATSB-weeks (10x1x4) and a household adherence of 50% (40/80).

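### If proportional hazards fails for time to first PCR infection, the protocol offers an adherence dose-response model as one of two unranked options and does not keep the comparison by allocation as the result

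*Protocol*

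**What the plan says.** Protocol Section 5 (Table 1) lists as a secondary efficacy endpoint "The time to first malaria infection assessed by PCR by the end of year-2" in the cohort children. Section 9.4.4.1.2 analyses it with a Cox model: "A shared frailty for study cluster and a 'fixed' effect coefficient for the study arm will be included". Results are to be given as a hazard ratio with confidence interval and p-value.

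The check is then described: "The proportional hazards assumption will be checked using plotting and regressing the Schoenfeld residuals against time after model fitting". No threshold is set. If the assumption is not met, "consideration of dose-response models with time-varying adherence measures will be considered", and the same sentence goes on to offer accelerated failure time models as an alternative. The two options are joined by *or*. Neither is ranked above the other and neither is committed to.

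On adherence, Section 7.7.2 says "Household-level adherence will be evaluated in the intervention cluster arms through ATSB monitoring visits". The measure is the ratio of actual to expected ATSB-time between visits about four weeks apart. Section 7.7.1 defines cluster adherence as keeping to the deployment schedule, with a delay of more than one month as the failure criterion. Section 9.4.2.1.1 fixes intention-to-treat for the primary outcome. Section 9.4.4.1.2 names no analysis population for this endpoint.

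**The concern.** The planned Cox model estimates the effect of being allocated to ATSB, and randomisation protects that contrast. A model on time-varying adherence estimates something else: how infection risk varies with the amount of bait coverage at the child's household. That coverage arises after randomisation and is recorded in one arm only.

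Self-selection is plausible on the protocol's own terms. A household head may refuse ATSBs (Section 7.3.3.2), and ATSB consent is not a cohort eligibility criterion (Section 7.3.2). A refuser's child allocated to ATSB would therefore carry zero dose, like a control. The protocol also plans to study whether ATSBs alter net use and treatment-seeking (Section 5.2.3). If households that keep their bait stations are at lower risk for other reasons, the adherence coefficient will show benefit where there is none.

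The choice between the two kinds of estimate would be triggered by the data, through a diagnostic without a threshold. At stake is the interpretation of one secondary efficacy endpoint. The primary analysis is untouched.

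**Working it through.** **No figure to reproduce.** The protocol gives no power, event count or hazard ratio for this endpoint. The check is a reading of the text plus a simulation.

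**Reading.** Section 9.4.4.1.2 does not say which adherence measure would be used. Of those defined, only household ATSB-time varies over time in a usable way; the cluster measure is a yes/no criterion over two years. Household ATSB-time has no counterpart in control clusters, so controls enter at zero.

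**Inputs from the protocol.** 80 clusters, 40 per arm; 67 children per cluster (67.2 in Section 7.8.1.1); six months of contributing follow-up, taken as six monthly intervals.

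**Assumptions not in the protocol.** Monthly hazard 0.15; cluster SD 0.4 on the log scale; mean adherence 0.85, SD 0.15, truncated to 0-1; log-risk SD between children 0.8 in the null runs; lower-risk households adhere better, with correlation 0, 0.3 or 0.6. There were 200 simulated trials per scenario.

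**Model.** A discrete-time form of the Cox model with cluster-robust standard errors:

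log(−log(1 − p)) = month effect + β·x

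Here x is either arm (0/1) or adherence (0-1, zero in controls). Rejection means |β/SE| > 1.96.

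**Check 1: no true effect.**

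| Adherence-risk correlation | Arm model: HR, rejection | Adherence in place of arm: HR (full v none), rejection | Adherence with arm also in the model: rejection |
|---|---|---|---|
| 0 | 1.00, 2.5% | 1.00, 3% | 4.5% |
| 0.3 | 0.99, 3.5% | 0.93, 13.5% | 100% |
| 0.6 | 1.00, 7.0% | 0.87, 37.5% | 100% |

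Simulation error at a true 5% is √(0.05 × 0.95 / 200) = 1.5 percentage points. The adherence rows at 0.3 and 0.6 lie well beyond it.

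A separate null simulation (300 trials per gradient) put adherence at 50%, 75% and 100% in thirds, with each step down carrying 1.1, 1.2 or 1.3 times the hazard. The adherence hazard ratios were 0.95, 0.93 and 0.89, with rejection of 7%, 14% and 26%. By allocation, rejection was 5-6%. The mildest case is within simulation error (√(0.05 × 0.95 / 300) = 1.3 points).

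These rates describe the adherence model whenever it is fitted. In the null runs of the first simulation, the time-interaction test for arm rejected in only 5.0%, 6.5% and 5.5% of trials (correlations 0, 0.3, 0.6). The rates therefore apply once the fallback is used, not to the plan as a whole.

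**Check 2: does it repair non-proportionality?** A time-interaction term was added to each model. The table gives the share of trials in which it was significant.

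| Cause | Set-up | Arm model | Adherence model |
|---|---|---|---|
| Waning coverage | mean adherence 0.85 × (1 − 0.15m), m = 0 to 5, so 0.85 falling to 0.21; HR at full adherence 0.7^(1/0.6) = 0.55 | 90.5% | 6.5% |
| Delayed effect, flat coverage | arm log HR rising linearly from 0 to 1.5 × log 0.7 | 100% | 99.5% |
| Depletion of susceptible children | HR at full adherence 0.7² = 0.49; log-risk SD between children 1.2 | 20.5% | 22% |

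The adherence model removes the problem in the first case and leaves it in the other two.

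**The case against.** The strongest case on the other side has four parts.

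- **Replacement is not stated.** A reader might infer that a failed check discards the randomised comparison. The text does not say so. It promises the arm hazard ratio without condition and only considers the alternatives. The same sentence offers accelerated failure time models, which do not need proportional hazards and can keep arm as the covariate. With controls at zero, an adherence model also still carries some randomised information. This stands. What remains is that nothing settles which estimate is the result.
- **The model can address non-proportional hazards.** A reader might infer that it never does. That is wrong: under waning coverage it does, and Section 9.4.1.1 itself anticipates changes in adherence. This stands, but the fallback is not limited to that cause, and Section 7.6.1.3 intends full coverage throughout.
- **The adherence measure is open.** Section 7.7 says "Since the intervention is deployed on a group basis rather than individually, adherence definitions will take account of this", so a cluster-level measure is possible, and the household confounding simulated here need not carry over to it in that form. This stands as a limit on the sizes. A cluster measure would still be post-randomisation.
- **The sizes rest on assumed inputs in one direction.** If higher-risk households adhered better, the bias would hide benefit instead. This stands too.

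A reader might also infer that infections are detected only at monthly visits, so that a Cox model is unsuitable from the start. Section 9.1.2.4 also collects blood spots at sick visits, so the documents do not support that premise. Handling of tied times is ordinary SAP detail.

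**Conclusion.** The point holds in a limited form. Section 9.4.4.1.2 admits a post-randomisation, one-arm adherence model as a data-triggered alternative to the comparison by allocation, without saying which is the result. Such a model changes the question and is open to confounding by household risk. It cures non-proportionality only where changing coverage is the cause.

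The inflation found, up to 37.5% rejection with no true effect, depends wholly on the assumed link between adherence and risk; with no link there was none. The protocol gives no value for that link, so the figures show direction and possible scale rather than a forecast. Severity is modest, because the analysis is contingent and the endpoint secondary.

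**What to change.** In Section 9.4.4.1.2, state that under non-proportional hazards the reported result remains a comparison by allocation, with a cluster frailty or random intercept. Name the method in advance. Suitable choices are a time-varying or interval-specific arm effect, the difference by arm in six-month cumulative infection or in restricted mean time, or an accelerated failure time model by arm.

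Keep adherence dose-response models if wanted, but label them supplementary and say that their coefficients are not effects of allocation.

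The cost is one paragraph of wording, with no new data and no change to sample size or follow-up.

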#### 9.4.4.2 *Analysis of the prevalence survey data*

The prevalence outcomes will be analysed using multi-level variance components models constructed on a log-binomial model with robust variance estimation. Random intercepts will be included for each study cluster, and the study arm will be included as a fixed effect. Model results will be presented as the risk ratio, 95% confidence intervals, and P-values.

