### 6.2.3 Measures to avoid contamination

Contamination or spillover effects between study arms may bias results towards the null. Therefore, the study will use a "fried egg" design. In intervention clusters, ATSBs will be deployed throughout the entire cluster. However, the effect will only be obtained from households located in the core of the cluster. Excluding measurement for the primary outcome in buffer zones will ensure that households in control villages are excluded that may benefit from a community effect from proximal households in neighbouring intervention villages.

[figure not shown]
The core area is defined as an area that is at least 300 to 600 meters from the perimeter of the cluster (i.e. at least 600 to 1200 meters between core areas of contiguous clusters), based on findings on the design of a recent cluster-randomized trial in Tanzania [19].

The buffer zones will be uniformly applied to each study cluster, including control clusters that do not border an intervention cluster or vice versa. This will be done to avoid the potential confounding factor of household distance from the cluster centre. For example, cluster borders may consist of a river or stream. The presence of water may result in a relatively higher or lower risk of malaria infection exposure compared to the core area, or the household density may differ between core and buffer areas, etc.

The boundaries for the core and buffer areas are based on recent mapping and census data.

Only the analysis of the data from the cohort study (primary outcome), parasite prevalence survey, and entomological monitoring will use the “fried egg” approach. The analysis of the passive facility-based or community-based surveillance data cannot use the fried-egg approach because only data on the village of residence, and not the geo-location of a household, is available in the routine clinical or CHV registers.

Figure 3: Buffer zone and core zone for sampling within each study cluster at trial sites with contiguous and non-contiguous cluster configurations

Notes: The core area for sampling will include all areas 300 to 600 meters from the cluster boundary, resulting in a 600 to 1200-meter buffer zone between the core intervention and core control clusters. ATSBs will be deployed throughout the entire intervention cluster, including the buffer zone. Buffer zones will be applied to all clusters (contiguous and non-contiguous).

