### 6.3.3 Epidemiological data

The epidemiological data sources for both the baseline and the main trial will include:

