#### 7.8.2.2 *Baseline*

A similar annual sample size of 44 per cluster, including 9 non-responders and 35 responders, will be used in 100 clusters during the baseline year before the deployment of ATSBs in the intervention arms.

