9.4.3.2 Computing of incidence rate ratios

To obtain incidence rate ratios, a multi-level variance compartments model will be used, constructed on a generalized linear model framework with a Poisson likelihood and a log link function. Random intercepts will be included for each study cluster, and study arm as a fixed effect coded categorically as 0 for arm A and 1 for arm B. The primary outcome will also be checked for the distributional assumption that the mean and variance of the outcome are similar after conditioning on cluster (e.g. are the within-cluster mean and variance similar). If the variance is substantially larger, a negative binomial likelihood will be considered. Results will be presented as the incidence rate ratio (IRR), 95% confidence intervals and *p*-value.

9.4.3.3 Covariable adjusted analysis of the primary and secondary outcomes:

A secondary co-variable adjusted analysis of the primary outcome will be conducted. Pre-specified covariables, developed and tested prior to final analysis, will be used. It is expected that these will also include the covariables used in restricted randomization (Table 4, below).

Variable	Categorization (if applicable)	Analysis	Analysis Population
Baseline prevalence	Calculated at cluster level	Clinical incidence, prevalence	ITT, per-protocol
Baseline incidence	Calculated at cluster level	Clinical incidence, prevalence	ITT, per-protocol
Rainfall (anomaly)	Summarized monthly at cluster level (lagged one month preceding) as anomaly	Clinical incidence, prevalence	ITT, per-protocol
Season		Clinical incidence, prevalence	ITT, per-protocol
Year	One vs Two	Clinical incidence, prevalence	ITT, per-protocol

Age	Under 60 months vs greater than 60 months	Clinical incidence, prevalence	ITT, per-protocol
-----	-------------------------------------------	--------------------------------	-------------------

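### The passive-case model leaves out each cluster's baseline case rate, and the main survey-prevalence model leaves cluster baseline prevalence to a secondary analysis, so both give up cheap precision

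*Protocol*

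**What the plan says.** **Models.** Section 9.4.4.2 (survey prevalence, log-binomial) and section 9.4.4.3 (passive cases, Poisson, or negative binomial if overdispersed) both state: "Random intercepts will be included for each study cluster, and the study arm will be included as a fixed effect". Neither section names a covariate.

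**Baseline data.** The household survey at its main-trial size, 35 responders per cluster, "will be used in 100 clusters during the baseline year before the deployment of ATSBs" (section 7.8.2.2). Section 6.3.3 opens with "The epidemiological data sources for both the baseline and the main trial will include", and passive surveillance is listed beneath it as 6.3.3.2. The timeline in section 12 (Table 8) has a separate row for baseline passive surveillance.

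**Adjusted analyses.** Section 9.4.3.3 is headed "Covariable adjusted analysis of the primary and secondary outcomes", but its text says "A secondary co-variable adjusted analysis of the primary outcome will be conducted". Table 4, in the same section, lists cluster-level baseline prevalence and cluster-level baseline incidence, each for "Clinical incidence, prevalence", in the ITT and per-protocol populations. Section 9.4.4.1.1 adds "Similar methods of analysis will be used to obtain crude and adjusted incidence ratios for secondary clinical outcomes", under the heading for secondary outcomes in the cohort.

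**The concern.** In a trial of 80 clusters, much of the variance of a community-level comparison comes from lasting differences between clusters. A pre-intervention measurement of the same outcome in the same cluster is usually the best predictor of those differences, and here it is already being collected.

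The gap is clearest for passive cases. Facility access, register completeness and community health volunteer activity differ between villages and tend to persist. The baseline incidence in Table 4 does not fill the gap, because Tables 2 and 3 both take baseline incidence from the baseline cohort. Section 6.2.3 also says "The analysis of the passive facility-based or community-based surveillance data cannot use the fried-egg approach", so buffer households stay in and spillover could weaken the contrast.

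For prevalence the issue is narrower. A baseline-adjusted analysis is listed, but the less precise crude model is the main one. The heading, sentence and table of 9.4.3.3 also disagree on which outcomes are adjusted. What is at stake is wider intervals than necessary on two secondary community-level endpoints, and chance baseline differences passing into the main estimates.

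**Working it through.** **1. Reproduce the plan's survey figure.** Inputs from section 7.8.2: 29.0% v 20.3%, ICC 0.05, 35 responders per cluster, 40 clusters per arm, two-sided alpha 0.05.

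- Design effect: 1 + 34 × 0.05 = 2.70. Responders per arm: 35 × 40 = 1,400.
- SE = √[(0.2059 + 0.1618) × 2.70 / 1,400] = 0.0266.
- z = 0.087 / 0.0266 = 3.27, so power = Φ(3.27 − 1.96) = 90.4% (90.3% with pooled variance).
- Sampling: 35 / 0.8 = 43.75, rounded to 44, and 44 × 80 = 3,520.

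The plan's 90% power and 3,520 participants are confirmed. Over two years (70 responders per cluster, design effect 4.45) z = 3.60 and power for the same contrast is 94.9%.

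**2. Effect of adjusting prevalence for cluster baseline.** A cluster-level covariate multiplies the variance by 1 − r², where r is the correlation between observed baseline and follow-up cluster prevalences.

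- Reliability of a cluster mean: R = m × ICC / [1 + (m − 1) × ICC].
- For m = 35: 1.75 / 2.70 = 0.648. For m = 70: 3.5 / 4.45 = 0.787.
- r = c × √(R_baseline × R_follow-up), where c is the correlation of true cluster levels between periods. The protocol does not give c, so it is shown as a range.
- Adjusted power = Φ(z / √(1 − r²) − 1.96).

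| Assumed c | r, one year | SE change | Power, one year | r, two years | Power, two years |
|---|---|---|---|---|---|
| unadjusted | – | – | 90.4% | – | 94.9% |
| 0.3 | 0.19 | −2% | 91.5% | 0.21 | 95.8% |
| 0.5 | 0.32 | −5% | 93.2% | 0.36 | 97.1% |
| 0.6 | 0.39 | −8% | 94.4% | 0.43 | 97.8% |
| 0.8 | 0.52 | −15% | 96.9% | 0.57 | 99.2% |
| 1.0 | 0.65 | −24% | 99.0% | 0.71 | 99.9% |

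In terms of detectable effect (pooled variance), the one-year reduction detectable with 90% power moves from 29.9% to 29.3%, 28.3% and 25.8% at c = 0.3, 0.5 and 0.8. The two-year figure moves from 27.3%, which is the plan's own, to 26.7%, 25.6% and 22.6%.

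**3. Passive cases.** Section 7.1 gives a county-wide 2016 rate, but the protocol states no planning rate, coefficient of variation or power for this endpoint. Only the relative gain can be shown. With r the assumed correlation between baseline and follow-up cluster rates, the SE is multiplied by √(1 − r²):

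- r = 0.3: √0.91 = 0.95, a fall of 5%.
- r = 0.5: √0.75 = 0.87, a fall of 13%.
- r = 0.7: √0.51 = 0.71, a fall of 29%.

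**4. Is the baseline passive rate used elsewhere?** It is not in 9.4.4.3, not in Table 4, and not among the candidate balancing factors in Table 3. Section 9.4.4.1.1 promises adjusted ratios only within the cohort heading.

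**The case against.** **The covariate list is open.** Section 9.4.3.3 says the covariables will be developed before the final analysis and are expected to include those used in the restricted randomisation. Section 9.4.2.2.2 leaves their definition to the SAP. So the baseline passive rate is unlisted rather than excluded. That is fair, but the model in 9.4.4.3 is stated, and nothing in the open list points to this covariate.

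**Prevalence adjustment is already planned.** A reader might infer from 9.4.4.2 that prevalence is analysed with arm and a cluster intercept only. Table 4 shows otherwise. A crude main estimate with an adjusted supportive one is valid and matches the approach to the primary outcome. What remains is a choice of which estimate leads, plus the inconsistent scope of 9.4.3.3.

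**The design already limits imbalance.** Table 3 offers baseline cohort incidence, net use, vaccination area, altitude and exact balance of clusters with a primary care facility. These are only candidate criteria, however, and none concerns register completeness. Balance in the design also leaves between-cluster variance in the standard error of a model that omits the balancing factors.

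**The gain is uncertain.** This stands. At a true correlation of 0.3 the one-year survey gains about 1 point of power. A large gain for passive cases would also need an assumed effect size and between-cluster variation. The only coefficient of variation in the protocol, 0.4, comes from the earlier trial used to size the cohort, not from registers.

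**Conclusion.** The point holds as one of efficiency on secondary endpoints. It is firmest for passive cases: baseline surveillance is collected, and no listed analysis uses the cluster's baseline rate. For prevalence, the useful covariate is planned but placed in the secondary analysis.

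Two stronger readings are tempting and not supported. One is that the tests are invalid or underpowered: the crude survey test meets its planned 90%, and no power is claimed for passive cases. The other is that adjustment would add 6 to 9 points of survey power. That needs true between-year correlations of 0.8 to 1.0. At 0.3 to 0.6 the one-year gain is about 1 to 4 points, and over two years it is about 3 to 4 points at 0.6 to 0.8.

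The survey results rest on the plan's own prevalence, effect and ICC plus an assumed correlation. The passive results rest on an assumed correlation alone. Dilution of the passive effect by buffer households is plausible, but the protocol does not quantify it.

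**What to change.** 1. In 9.4.4.3, add the cluster's log baseline passive case rate as a fixed covariate and list it in Table 4 for that endpoint. Build it from the same registers, and define its denominator consistently with follow-up, since section 6.3.3.2 allows denominators to be updated.
2. In 9.4.4.2, make the model adjusted for cluster baseline RDT prevalence the main estimate and keep the crude model as supportive.
3. In 9.4.3.3, make the heading, sentence and Table 4 agree on which secondary outcomes are adjusted, and say whether clinical incidence in Table 4 includes passive cases.

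The cost is wording and one extra term per model, with 80 clusters to support it and no new data collection. The main estimates become conditional on baseline. The change should be fixed before allocation is revealed to the analysts.
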